3.1 Inclusion Criteria

- 3.1.1 Subject must have histologically or cytologically confirmed locoregionally recurrent squamous cell carcinoma of the head and neck (including any primary site, such as oral cavity, oropharynx, larynx or hypopharynx, and nasopharynx carcinoma)
 - 3.1.2 Must be a candidate for salvage surgery
 - 3.1.3 Willing to provide blood and tissue from diagnostic biopsy and at the time of surgery
 - 3.1.4 Has documented disease-free interval (DFI) > 8 weeks after completion of initial therapy; DFI is from the time of completion of initial treatment (from date last known disease-free at end of initial treatment) to the diagnosis of local or locoregional recurrence
 - 3.1.5 Any HPV status or smoking history is permitted. Oropharyngeal cancer patients are required to undergo HPV testing with p16 immunohistochemistry and/or confirmatory HPV PCR or ISH testing
 - 3.1.6 Age 18 years or older
 - 3.1.7 ECOG performance status ≤ 2 (Karnofsky $\geq 60\%$, see Appendix A)
 - 3.1.8 Participant must have normal organ and marrow function as defined below within 21 days prior to study registration:
 - leukocytes $\geq 3,000/\text{mcL}$
 - absolute neutrophil count $\geq 1,500/\text{mcL}$
 - platelets $\geq 100,000/\text{mcL}$
 - total bilirubin $\leq 2.0 \text{ g/dL}$
 - AST(SGOT)/ALT(SGPT) $\leq 2.5 \times$ institutional upper limit of normal
 - creatinine within normal institutional limits
- OR
- creatinine clearance $\geq 60 \text{ mL/min/1.73 m}^2$ (calculated using the Cockcroft-

Gault equation) for participants with creatinine levels above institutional normal

- 3.1.9 Ability to understand and the willingness to sign a written informed consent document
- 3.1.10 Women of childbearing potential (WOCBP) must agree to use appropriate method(s) of contraception. WOCBP should plan to use an adequate method to avoid pregnancy for 5 months (30 days plus the time required for nivolumab to undergo five half-lives) after the last dose of investigational drug
- 3.1.11 Women of childbearing potential must have a negative serum or urine pregnancy test (minimum sensitivity 25 iu/l or equivalent units of hcg) within 24 hours prior to the start of nivolumab

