4. REGISTRATION PROCEDURES

4.1 General Guidelines for DF/HCC Institutions

An investigator will confirm eligibility criteria and a member of the study team will complete the protocol-specific eligibility checklist.

Eligible subjects will be registered by a member of the study team in the Clinical Trials Management System (CTMS) “OnCore”. Registrations must occur prior to the initiation of protocol therapy. Any subject not registered to the protocol before protocol therapy begins will be considered ineligible and registration will be denied.

Following registration, participants may begin protocol therapy. Issues that would cause treatment delays should be discussed with the Overall Principal Investigator (PI). If a participant does not receive protocol therapy following registration, the participant’s registration on the study must be canceled. Registration cancellations must be made in OnCore as soon as possible.

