At the time of pre-treatment biopsy and surgical resection, two cores of fresh tissue will be allocated to two 1.5 mL centrifuge tubes (one core in each tube) in RPMI containing 10% fetal bovine serum (FBS). Additionally, at the time of pre- and post-treatment biopsy and at specified time points during and after treatment, two tubes of peripheral blood (obtained at a minimum of 3 time points during the study) will be obtained per standard collection protocols – drawn in phlebotomy or clinic and captured in 8 mL whole blood, purple top tubes. The volume of blood to be collected per blood draw for study purposes will not exceed 40 mL. All specimens will be de-identified and labeled with the participant's initials, study ID number and the date of acquisition. After collection, the tissue and blood collection tubes should be delivered immediately to the lab of [name] and [name] [office: LC-4315J, Robert and Renee Belfer Center for Applied Cancer Science, [name], [contact] or [contact]]. The specimen must arrive in a timely fashion to facilitate processing for evaluation of immune cells. Tissue will be prepared as a cell suspension that will be stained using fluorescently-conjugated antibody cocktails for human immune markers (surface antibodies include: CD45, CD3, CD4, CD8, CD69, CD38, CCR7, LAG-3, TIM-3, PD-1, CD45RA, HLA-DR, CTLA-4, CD16, CD56, CD31, CD33, PD-L1, PD-L2, GITR, CD15, CD19, and CD14). Cells will be analyzed within 72 hours of fixation on a BD Fortessa cell analyzer with FACSDiva software v8.0.1 (BD Biosciences) and gated using FlowJo software v10.

Immunohistochemistry

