10. STUDY CALENDAR

Screening evaluations are to be conducted within 3 weeks prior to study registration. Procedures done within a week of study registration don't need to be repeated to establish baseline. Scans and x-rays must be done ≤ 4 weeks prior to the start of therapy. Laboratory evaluations do not need to be repeated to meet eligibility criteria on cycle 1 day 1, if they were done within 3 days of the first treatment dose. In an event that the participant's condition is deteriorating, laboratory evaluations should be repeated within 48 hours prior to initiation of the next cycle of therapy. Each treatment cycle in this study is 28 days long.

Assessments must be performed prior to administration of any study agent. Study assessments and agents should be administered within ± 3 days of the protocol-specified date, unless otherwise noted.

	Screening	Window Phase	Pre-surgery	Surgery	Adjuvant phase							End of Treatment	Follow up visit 30 days after last dose
					Cycle 1		Cycle 2		Cycle 3		Cycle 4-6		
					Day 1	Day 15	Day 1	Day 15	Day 1	Day 15	Day 1		
Informed consent	X												
Medical History	X												
Concomitant Medicines	X												
Physical exam (Ht, Wt, VS, PS) ^a	X	X			X	X	X	X	X	X	X	X	X
Routine labs ^b	X	X			X	X	X	X	X	X	X	X	X
FSH (if female <55 years old)	X												
HPV testing (oropharyngeal only)	X												
B-HCG (WOCBP only) ^c	X									X	X		
ECG	X									X	X		

Radiologic evaluation ^{d, g}	X		X	X								
Biopsy sample ^{e, f}	X										X ^h	
Correlative biopsy ^f	X										X ^h	
Correlative blood ⁱ	X ⁱ					X					X	
Nivolumab		X		X	X	X	X	X	X	X		
Lirilumab		X		X		X		X		X		
Adverse event evaluation		X		X	X	X	X	X	X	X	X	X

- a) Physical exam is symptom directed. Height measured at screening only.
- b) Routine labs include: CBC, LFTs, CMP, Mg, TSH, Free T4. Baseline HCV antibody, hepatitis B surface antigen, hepatitis B surface antibody, and hepatitis B core antibody testing is required. TSH and free T4 are required less frequently according to the following schedule: screening, window phase (D1 of pre-surgery immunotherapy dosing), D1 of each adjuvant cycle, and at the 30-day post protocol treatment visit.
- c) Serum or urine within 24 hours prior to first dose.

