- d) PET-CT or contrast-enhanced CT imaging of the chest, abdomen and pelvis will be obtained at baseline to rule out distant disease. Contrast-enhanced neck CT or MRI at the time of screening or registration and will be repeated 1-4 days prior to salvage surgery. Interval scans (contrast-enhanced neck CT or MRI) will be performed every 8 weeks following salvage surgery or as clinically indicated while on treatment. Follow-up imaging will be performed at the end of treatment (see footnote g).
- e) Archival tissue is acceptable. Some of this tissue will also be used for correlative study.
- f) Fresh biopsy is mandatory if tumor is accessible. Fresh tissue is also collected at the time of surgery. Biopsy will also be obtained at the time of progression or recurrence, if safe to perform.
- g) Participants, regardless if they receive the adjuvant therapy, will be followed for response (at the end of the window phase of the trial) until first disease progression or recurrence and for survival throughout the trial for a total of 5 years from time of salvage surgery (or from study registration if no salvage surgery was performed). Post-end of protocol treatment, if first disease progression or recurrence has not been confirmed, tumor assessments (contrast-enhanced neck CT or MRI and PET-CT) are to continue every 3 months (+/- 1 month) until first disease progression or recurrence, death, or 2 years post-date of salvage surgery (or from study registration if no salvage surgery was performed), then every 6 months until 5 years post-date of salvage surgery (or from study registration if no salvage surgery was performed). After first disease progression or recurrence has been confirmed, patients will be followed for survival by phone only, every 3 months (+/- 1 month) until death or 5 years post-date of salvage surgery (or from study registration if no salvage surgery was performed), whichever occurs first.
- h) Recommended in the setting of disease recurrence or progression only.
- i) Screening correlative blood collection may occur at screening or at pre-surgery. Pre-surgery correlative blood collection may occur any time from the day following neoadjuvant drug administration until surgery. EOT blood draw may occur after the EOT visit.

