For secondary objectives: Best overall response (at the end of the window phase of the trial) will be summarized as a proportion with a corresponding exact 95% confidence interval (CI) (noting that a 'modified' version (no confirmation of initial CR or PR) of RECIST will be used for patients whose disease initially achieves a CR or PR: the patients' tumor will be resected prior to confirming the CR or PR at least 4 weeks after initial response). Adverse events will be classified and graded according to the CTCAE v.4.0. Frequencies of adverse events will be summarized. The distributions of n-year DFS and survival will be estimated using a Kaplan-Meier method with corresponding 95% confidence intervals for time-specific event time. Several correlative studies are also planned. Given the small sample size of this trial, these studies are exploratory. Samples will be collected at baseline and at post-baseline timepoints as outlined in the protocol. Markers from the samples (cluster differentiation markers from both tumor and circulating peripheral blood, see Section 9.1) will be summarized descriptively and graphically. Within subject changes in markers will also be analyzed. Assuming n=50 patients with useable baseline and post baseline markers, there is 81% power to detect .42 SD mean difference (Wilcoxon sign rank test two-sided 0.05 alpha level).

The following stopping rule will be used to monitor delays in salvage surgery due to excessive nivolumab and/or lirilumab-related toxicity: if 3 or more of the first 10 patients who begin protocol treatment experience treatment related toxicities which cause delays in definitive surgery, accrual to the trial will be suspended to further evaluate the events and decisions made regarding the overall status of the trial. If the true delay in surgery rate due to toxicity is 10% then the probability of suspending accrual is 7%; if the true rate is 20%, then the probability of suspending accrual is 32.2%; if the true delay in surgery rate due to toxicity is 30% then the probability of suspending accrual is 62%. Adverse events will be continuously monitored

throughout the trial by the study team with decisions made accordingly regarding the study status and patient entry throughout the duration of the trial.

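### Footnote i of the study calendar lets the baseline correlative blood be drawn after the window dose, and Section 13 has no rule for such samples

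*Combined protocol and SAP*

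**What the plan says.** Footnote i to the study calendar (Section 10) has two consecutive sentences on this point: "Screening correlative blood collection may occur at screening or at pre-surgery" and "Pre-surgery correlative blood collection may occur any time from the day following neoadjuvant drug administration until surgery".

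Other parts of the plan place the first sample before treatment:

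- Section 10, opening text: "Screening evaluations are to be conducted within 3 weeks prior to study registration", and "Assessments must be performed prior to administration of any study agent".
- Section 4.1: "Registrations must occur prior to the initiation of protocol therapy".
- Section 9.1, flow cytometry: blood is taken "at the time of pre- and post-treatment biopsy and at specified time points during and after treatment, two tubes of peripheral blood".
- Inclusion criterion 3.1.3: "Willing to provide blood and tissue from diagnostic biopsy and at the time of surgery".

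Section 13 plans descriptive summaries and within-subject change analyses of markers from tumor and peripheral blood, calls them exploratory, and refers to the protocol for sample timing. Its power statement is: "Assuming n=50 patients with useable baseline and post baseline markers, there is 81% power to detect .42 SD mean difference", using a two-sided 0.05 Wilcoxon signed-rank test. It does not define baseline or useable.

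**The concern.** Read together, the two sentences of footnote i allow the sample labelled screening to be collected only after both study drugs have been given. A patient handled that way would have no pre-dose blood, and it could not be obtained later. Section 2.5 makes early change in peripheral blood immune parameters one of the questions the window phase should address, so the pre-dose sample is the reference for that question.

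Section 13 defers to the calendar for timing, and the calendar is where the ambiguity lies. The choice of whether to count a post-dose sample as baseline would be made at analysis, possibly with the data in view. The two options do different damage:

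- **Keep the sample as baseline.** A sustained marker change is diluted. A transient rise that is present at the draw and gone later appears as a fall that never happened.
- **Drop the patient.** The number of pairs falls.

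The transient case has some support in the protocol. CD69 is in the flow panel (Section 9.1), and Section 2.3.1.2 reports a transient rise in NK-cell CD69 with the earlier anti-KIR antibody.

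**Working it through.** **1. Timing.** Section 5.2 gives one dose of each drug 7 to 21 days before surgery. Footnote i runs pre-surgery collection from the day after that dose until surgery, so a screening sample taken at pre-surgery falls between day 1 and about day 21 after dosing. Section 2.2.1.1 gives a nivolumab half-life of 26.7 days. On simple exponential decay, the fraction remaining at day 21 is 0.5^(21/26.7) = 0.58. Section 2.3.1.1 reports KIR occupancy above 90% for more than 2 weeks at 1 and 3 mg/kg of the earlier antibody. Such a sample is taken with drug on board.

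**2. The plan's own figure.** Inputs from Section 13: n = 50 pairs, difference 0.42 SD, two-sided α = 0.05, signed-rank test. With normal differences, the signed-rank test behaves like a paired t-test on n × 3/π pairs:

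- effective n = 50 × 3/π = 47.7
- noncentrality = 0.42 × √47.7 = 2.90
- power from the noncentral t = 81.1%

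Simulating the signed-rank test directly (40,000 replicates, unit-SD changes) gives 81.2%. The stated 81% is correct for 50 valid pairs.

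**3. Post-dose sample used as baseline, sustained marker.** The affected share f is not in the documents and is assumed to be 10–50%. Carry-over c is the part of the change already present at the draw, assumed to be half or all. Affected patients then have mean change 0.42 × (1 − c), and the average is 0.42 × (1 − f × c). Power is simulated as in step 2, with n = 50.

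| Affected | Mean change, c = ½ | Power, c = ½ | Mean change, c = 1 | Power, c = 1 |
|---|---|---|---|---|
| 0 | 0.42 | 81% | 0.42 | 81% |
| 5 (10%) | 0.40 | 77% | 0.38 | 72% |
| 10 (20%) | 0.38 | 72% | 0.34 | 61% |
| 15 (30%) | 0.36 | 67% | 0.29 | 50% |
| 25 (50%) | 0.32 | 57% | 0.21 | 28% |

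**4. Affected patients excluded.** The effect stays at 0.42 SD and only n falls.

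| Pairs left of 50 | Power, simulated | Power, formula of step 2 |
|---|---|---|
| 45 | 76% | 77% |
| 40 | 72% | 72% |
| 35 | 65% | 65% |
| 25 | 50% | 50% |

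By the same formula, the difference detectable with 81% power rises from 0.42 SD at 50 pairs to 0.47 SD at 40.

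**5. Post-dose sample used as baseline, transient marker.** Assume no lasting change and a post-dose baseline raised by 0.42 SD. Affected patients then have mean change −0.42 SD and the others 0. The nominal 5% rejection rate becomes 5.6%, 8.1%, 12.7% and 27.8% with 10%, 20%, 30% and 50% affected. As a check, the 50% case mirrors the 50% full carry-over case in step 3, and the two agree (27.8% and 28.0%).

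A separate run of 20,000 replicates matched the power figures in steps 2 to 4 to within about one percentage point.

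**The case against.** The best defence is that footnote i was meant to describe separate draws at screening, before surgery and at end of treatment. That fits Section 9.1, which asks for at least three blood time points. Footnote b also uses the term pre-surgery for the window dosing day itself, so the permitted delay might reach only to that visit. This may have been the intent, but footnote i defines its own pre-surgery window, starting the day after dosing, and the calendar has a separate Pre-surgery column. The words as written permit the substitution. The calendar row itself may be damaged in extraction, so nothing here rests on which cells are marked.

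Several narrower points stand:

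- The rule that assessments precede any study agent can be read visit by visit, and a specific footnote can qualify a general rule. Criterion 3.1.3 concerns willingness and sets no draw time. The direct conflicts are with the pre-treatment blood in Section 9.1 and with the sequence of screening, registration, then therapy.
- In ordinary use baseline means before treatment, and the word useable hints at exclusion. Neither amounts to a rule.
- Section 13 registers 58 patients and assumes 50 useable pairs. Counted from 58, a 10% loss leaves about 52 and a 20% loss about 46, so exclusion would cost less than step 4 shows if nothing else were lost. The same eight patients must also cover ineligibility, failure before surgery and failed samples.
- Affected share, carry-over and the size of a transient rise are all assumptions. The CD69 observation comes from another antibody in leukemia patients, and the protocol does not say how long the rise lasted. A draw near day 21 might miss it.
- The analysis is exploratory.

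These points limit the size of the problem. They do not remove the contradiction.

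**Conclusion.** The concern holds. As written, footnote i can leave a patient without pre-treatment blood, contrary to Section 9.1 and to Sections 10 and 4.1 read together, and Section 13 does not say what to do with such a sample. The 81% power figure is not itself wrong, but it depends on 50 valid baselines.

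The size depends on how often the option is used, which the documents do not give, and the wording is permissive. At an assumed 10% affected, the loss is about 4 to 9 points of power if the samples are kept and about 5 if they are dropped from the 50. At 30% or more, the comparison is clearly weakened, or for a transient marker clearly biased. The consequence is confined to exploratory blood markers. The plan should be corrected because the lost information cannot be recovered and the correction is small, not because any main endpoint is at risk.

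**What to change.** - Amend footnote i so that baseline correlative blood is drawn before the window-phase infusion, either at screening or with the window-phase labs before the first drug.
- Keep the pre-surgery draw as a separate, post-dose time point.
- Add one line to Section 13 defining a useable baseline as a pre-dose sample.
- Label any sample already taken only after dosing as post-dose, leave it out of the change-from-baseline analysis, and report how many patients this removes.

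The cost is one footnote sentence and one line in Section 13. No visit is added, because routine labs are already scheduled in the window phase. Sample logistics become slightly tighter, given the weekend processing limits in Section 9.1 and the same-day shipping from outside sites in Section 9.2.

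Leaving out existing post-dose samples does not always gain power. With half carry-over it gives 72% against 72% at 20% affected, and 50% against 57% at 50% affected. With full carry-over it gains: 72% against 61%, and 50% against 28%. In either case the benefit is an estimate of change that is not diluted and has a clear meaning.

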2.3.1.2 Clinical safety

A phase I study of IPH-2101 in 23 elderly patients with acute myeloid leukemia (AML) in first complete remission was recently reported. Patients received escalating doses: 0.0003, 0.003, 0.015, 0.075, 0.3, 1 and 3 mg/kg, but a maximally tolerated dose was not reached. At the highest

dose levels (0.3, 1, and 3 mg/kg), transient increases in tumor necrosis factor-alpha (TNF- α) serum concentrations and NK cell CD69 expression were observed. Grade 3 and 4 adverse events were limited to one patient who experienced a transient lipase elevation that resolved spontaneously. The most frequently reported treatment-related effects included pruritis (17%), rash (17%), and fever (13%). A similar trial in 32 patients with relapsed, refractory multiple myeloma used IPH-2101 administered IV every 28 days in 7 dose-escalated cohorts (0.0003 to 3 mg/kg) for up to 4 cycles. Again the highest dose was tolerated without achieving a maximally tolerated dose [31]. In the relapsed, refractory myeloma setting there was one severe adverse event reported (acute renal failure requiring hemodialysis), with no evidence of autoimmunity noted. In the expanded cohort of this trial, the most commonly observed treatment-related effects included fatigue, chills, non-cardiac chest pain and pyrexia.

IPH-2101 has also been evaluated in combination with lenalidomide in the treatment of relapsed, refractory multiple myeloma [32]. In a phase I trial that enrolled 15 patients in three cohorts lenalidomide was given at a standard 10 mg dose in cohort 1 and 25 mg in cohorts 2 and 3 on days 1 to 21 of a 28 day cycle in combination with IPH-2101 given IV on day 1 of each cycle at 0.2 mg/kg in cohort 1, 1 mg/kg in cohort 2, and 2 mg/kg in cohort 3. The biologic endpoint of full KIR occupancy was achieved across the IPH-2101 dosing interval. Pharmacokinetic data of IPH-2101 with lenalidomide were similar to data from a prior single-agent IPH-2101 trial. Five serious adverse events were reported along with five objective responses; with no autoimmunity reported. Grade 3 and 4 adverse events most often included neutropenia and lymphopenia, along with a cytokine release syndrome with elevation in pro-inflammatory cytokines in two patients. After completion of the study, one patient developed therapy-related myelodysplasia.

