5.2 Treatment Regimen

Patients will be premedicated with diphenhydramine, famotidine, and acetaminophen before lirilumab doses unless otherwise directed by treating investigator. Each treatment cycle will be 28 days long. On the days when both nivolumab and lirilumab are administered, nivolumab will be administered first, followed by lirilumab, with a 30-minute minimum duration time between the administration of nivolumab and lirilumab. Nivolumab infusion must be promptly followed by a saline flush to clear the line of nivolumab before starting the lirilumab infusion. Participants should be carefully monitored for infusion reactions during nivolumab and lirilumab administration. If an acute infusion reaction is noted, participants should be managed according to the algorithm described in Appendix C or in Nivolumab IB.

Nivolumab infusion time should be 30 (+/-10) minutes. A volumetric pump with a 0.2 - 0.22 micron in-line filter through an IV transfer set will be used.

Lirilumab infusion time should be 60 (+/-15) minutes. A volumetric pump with a 0.2 micron in-line filter through an IV transfer set will be used.

Window phase: Seven to twenty-one days prior to salvage surgical resection, a single dose of each study drug will be administered. Nivolumab 240 mg IV flat dosing will be administered through IV infusion, followed by lirilumab 240 mg IV flat dosing.

Salvage surgical resection: Each participant should be a candidate for salvage surgical resection to be able to participate in this study. Surgery should be performed no later than 4 weeks after study enrollment. Patients remain eligible to continue on study regardless of post-salvage surgery excisional margin status. Following salvage surgery, re-irradiation or additional chemotherapy is not permitted during the study period.

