5.6 Criteria for Taking a Participant Off Protocol Therapy

The following stopping rule will be used to monitor delays in salvage surgery due to excessive nivolumab and/or lirilumab-related toxicity: if 3 or more of the first 10 patients who begin protocol treatment experience treatment related toxicities which cause delays in definitive surgery, accrual to the trial will be suspended to further evaluate the events and decisions made regarding the overall status of the trial. If the true delay in surgery rate due to toxicity is 10% then the probability of suspending accrual is 7%; if the true rate is 20%, then the probability of suspending accrual is 32.2%; if the true delay in surgery rate due to toxicity is 30% then the probability of suspending accrual is 62%. Adverse events will be continuously monitored throughout the trial by the study team with decisions made accordingly regarding the study status and patient entry throughout the duration of the trial.

Any adverse event(s) (as outlined in Section 6.1) attributed to the study medication that result in a delay in the planned date of salvage surgery exceeding 14 days warrants removal of the patient from the study protocol treatment. Otherwise, therapy can be resumed in the adjuvant phase at the discretion of the treating physician or PI. Duration of therapy will depend on individual response, evidence of disease progression or recurrence and tolerance. In the absence of treatment delays in the adjuvant phase due to adverse event(s), treatment may continue for six cycles or until one of the following criteria applies:

- Disease progression or recurrence
- Intercurrent illness that prevents further administration of treatment
- Unacceptable adverse event(s) (see Section 6.2)
- Participant demonstrates an inability or unwillingness to comply with the medication regimen and/or documentation requirements
- Participant decides to withdraw from the protocol therapy
- General or specific changes in the participant's condition rendering the participant unacceptable for further treatment in the judgment of the treating investigator

Participants will be removed from the protocol therapy when any of these criteria apply. The reason for removal from protocol therapy, and the date the participant was removed, must be documented in the case report form (CRF). Alternative care options will be discussed with the participant.

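### The post-dose correlative blood may be drawn on any day from dosing to surgery, so blood and tumor changes may be compared at different times with no account of days since dose

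*Combined protocol and SAP*

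**What the plan says.** Section 5.2 sets the window phase: "Seven to twenty-one days prior to salvage surgical resection, a single dose of each study drug will be administered". For the blood that follows this dose, footnote i of the Study Calendar (Section 10) says: "Pre-surgery correlative blood collection may occur any time from the day following neoadjuvant drug administration until surgery". The calendar's general tolerance does not narrow this, because it gives way to specific notes: "Study assessments and agents should be administered within ± 3 days of the protocol-specified date, unless otherwise noted".

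Section 9.1 places the blood differently: "at the time of pre- and post-treatment biopsy and at specified time points during and after treatment, two tubes of peripheral blood" are to be obtained, and these are "obtained at a minimum of 3 time points during the study". The same section collects fresh tissue at the pre-treatment biopsy and at surgical resection, and has specimens labeled with their acquisition date.

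Section 2.5 gives the purpose: to learn whether the circulating immune profile reflects the tumor, and whether early blood changes could signal response without repeat biopsies. Section 13 calls the correlative studies exploratory and states: "Within subject changes in markers will also be analyzed". It assumes 50 patients with usable baseline and post-baseline markers and quotes 81% power for a 0.42 SD mean difference (Wilcoxon signed-rank, two-sided 0.05). It names no reference day and no adjustment for time since dose.

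**The concern.** Comparing change in blood with change in tumor needs the two post-dose samples to reflect the same period of drug exposure. The tumor sample is fixed at surgery. Under footnote i the blood sample is not: one patient may be bled the day after dosing and another on the morning of surgery. If blood and tumor then fail to agree, the reason could be biology or scheduling, and the planned analysis cannot tell which. Samples cannot be re-timed afterwards.

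A second, conditional concern is dilution. Section 2.3.1.2 reports that, at the higher doses of the predecessor anti-KIR antibody, transient increases in TNF-alpha "serum concentrations and NK cell CD69 expression were observed". CD69 is on this trial's flow panel. If a marker rises and falls within the window, draws spread across that window would average high and low values, and the mean change would shrink.

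**Working it through.** **1. Width of the window.** Earliest draw: day 1 (footnote i). Latest draw: the day of surgery, planned for day 7 to day 21 (Section 5.2). Days since dose therefore range from 1 to 21, and the largest planned blood-to-tissue gap is 21 − 1 = 20 days. Day 21 is a planned limit only. Section 5.6 contemplates surgery slipping for toxicity, since only a "delay in the planned date of salvage surgery exceeding 14 days warrants removal of the patient from the study protocol treatment".

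**2. The two texts side by side.** Section 9.1 links blood to the pre- and post-treatment biopsy. The natural reading of the latter is the surgical specimen, the only post-dose tissue planned for every patient who has surgery. Footnote i removes that link. A site can follow footnote i and depart from Section 9.1.

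**3. The plan's power figure.** Inputs from Section 13: n = 50, effect 0.42 SD, two-sided 0.05.
- Effective n for the signed-rank test under normality: 50 × 3/π = 47.7.
- Noncentrality: √47.7 × 0.42 = 2.90. Critical t: 2.01.
- Power: 0.811. Simulating the signed-rank test (40,000 runs) gives 0.813.

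The stated 81% is reproduced.

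**4. What dilution could do (assumed scenarios).** Suppose a fraction f of draws falls when the effect is zero and the rest see 0.42 SD. The standardized effect becomes (1 − f) × 0.42 / √(1 + f(1 − f) × 0.42²).

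| f | Standardized effect | Power, n = 50 (simulated) |
|---|---|---|
| 0 | 0.42 | 81% |
| 10% | 0.375 | 72% |
| 25% | 0.310 | 56% |
| 50% | 0.206 | 28% |

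No document gives a value for f. A marker that is stable over the window has f = 0.

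**5. What re-timing the draw does to early capture.** Assume surgery is equally likely on each of days 7 to 21. Take assumed changes lasting 3 or 7 days; the documents give no duration.
- As written, with the draw equally likely on each day from 1 to surgery (S): the average of 3/S over S = 7 to 21 is 24%, and of 7/S is 56%.
- Draw 1-4 days before surgery, each of the 15 × 4 = 60 combinations equally likely: 1/60 = 2% and 14/60 = 23%.
- Draw on the day of surgery: 0/15 = 0% and 1/15 = 7%.

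The planned blood-to-tissue gap falls from as much as 20 days to at most 4. Days since dose would still run from 7 − 4 = 3 to 21 − 1 = 20, or from 7 to 21 if drawn on the day of surgery. Re-timing alone does not standardize exposure.

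**The case against.** The strongest reply is that the stakes are small and the flexibility deliberate. Section 13 declares these analyses exploratory. Sections 9.1 and 9.2 limit weekend processing and require same-day shipping, so a loose window protects sample yield. At least three blood time points are required, and Section 13 speaks of post-baseline time points in the plural, so the pre-surgery draw is not the only one. Acquisition dates are on the labels, so days since dose can be derived without new data. All of this stands and limits the severity. It does not remove the point: only the pre-surgery blood can pair with the surgical specimen, and a date that can be derived does not help until the analysis uses it.

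Three stronger inferences are tempting, and the documents do not support them.
- A reader might infer that the protocol's own data show key immune changes to be transient. The evidence is one sentence on two readouts of the predecessor antibody in AML. TNF-alpha is not on the flow panel, and CD69 is one marker among many. In the other direction, Section 2.3.1.1 reports KIR occupancy above 90% for more than 2 weeks at 1 and 3 mg/kg, and Section 2.2.1.1 gives nivolumab a half-life of 26.7 days.
- A reader might infer that the 81% power is overstated. It is conditional on a 0.42 SD difference and is correct for that. Dilution would make the true difference smaller and would leave the calculation valid. The calculation also covers tumor markers, whose post-dose sample is fixed at surgery.
- A reader might infer that moving the draw nearer to surgery recovers short-lived effects. Step 5 shows the reverse.

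**Conclusion.** The point holds as a problem of pairing and interpretation in an exploratory analysis. Footnote i and Section 9.1 disagree on when the post-dose blood is taken. As footnote i stands, blood and tissue can be up to 20 days apart on the planned schedule, and Section 13 takes no account of days since dose. The comparison posed in Section 2.5 may therefore be confounded by draw timing.

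Dilution of short-lived markers is possible. It is plausible for NK-cell CD69, but it is not established and cannot be sized from the documents. The losses in step 4 illustrate assumed fractions and are not estimates. Severity is low: the primary endpoint, 1-year DFS, is untouched, and the correction is cheap if made before samples are collected.

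**What to change.** 1. **Footnote i (Section 10):** tie the post-dose draw to the existing scan visit 1-4 days before surgery, or to the day of surgery, and align the wording with Section 9.1 so that each blood sample pairs with the surgical tissue.
2. **Section 13:** analyze blood-marker change with days since dose, from the recorded acquisition date, as a covariate. This is needed even after change 1 because surgery itself varies over days 7-21. The signed-rank test takes no covariate, so add a regression of change on centered days since dose and keep the signed-rank test as the unadjusted summary.
3. **In the same edit:** footnote i also lets the screening blood be taken at pre-surgery. State that the baseline sample must precede the first dose, so that it cannot be read as allowing a post-dose baseline.

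Cost: wording changes and one model term, with no added visit or tube. There are two downsides: less freedom in scheduling one draw, and less frequent capture of early transient changes. The change serves blood-tissue pairing and interpretability. It does not serve detection of short-lived effects, and the plan should say so.
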